11.2 Assessment of Seriousness

The assessment of seriousness of safety events should be performed by an appropriately delegated, medically qualified member of the site research team.

A safety event is assessed as serious if it:

- · Results in death;
- Is life threatening, i.e. the investigator considers the event places the subject at immediate risk of death from the experience as it occurred (this does not include an adverse experience that, had it occurred in a more severe form, might have cause death);
- Requires hospitalisation or prolongation of existing hospitalisation (hospitalisation is defined as an inpatient admission, regardless of length of stay, even if the hospitalisation is a precautionary measure for continued observation. Hospitalisations for a pre-existing condition, including elective procedures that have not worsened, or hospitalisations for pulmonary exacerbations, including prolonged existing hospitalisation for pulmonary exacerbation, do not constitute a SAE);
- Results in persistent or significant disability or incapacity (substantial disruption of one's ability to conduct normal life functions);
- · Consists of a congenital anomaly or birth defect (in offspring of subjects, or their partners, taking the product regardless of time of diagnosis);
- Other important medical events (these may not result in death, be life-threatening, overdose, secondary malignancy or require hospitalisation, but may be considered a serious adverse event/experience when, based upon appropriate medical judgment, they may jeopardise the subject and may require medical or surgical intervention to prevent one of the outcomes listed in this definition).

11.3 Severity of Adverse Events

All adverse events should be assessed for severity. The assignment of the severity/grading should be made by the investigator responsible for the care of the participant using the definitions in the table below:

Table 1: Severity Grading

IRAS ID: 293186 Page **40** of **63**

Severity	Description	
Mild	Does not interfere with routine activities.	
Moderate	Interferes with routine activities.	
Severe	Impossible to perform routine activities.	

N.B. A distinction is drawn between **serious** and **severe** AEs. Severity is a measure of intensity (see above) whereas seriousness is defined using the criteria in Section 11.2. Hence, a severe safety event need not necessarily be a "serious" safety event.

11.4 Assessment of "Causality" – Relationship to Trial Treatment/Intervention

The assignment of the causality should be made using the definitions in the table below:

Table 2: Definitions of Causality

Relationship	Description	
Unrelated	There is no evidence of any causal relationship.	
	N.B. An alternative cause for the AE should be given	
Unlikely	There is little evidence to suggest there is a causal relationship (e.g. the event	
	did not occur within a reasonable time after administration of the trial	
	medication). There is another reasonable explanation for the event (e.g. the	
	participant's clinical condition, other concomitant treatment).	
Possibly	There is some evidence to suggest a causal relationship (e.g. because the	
	event occurs within a reasonable time after administration of the trial	
	medication). However, the influence of other factors may have contributed to	
	the event (e.g. the participant's clinical condition, other concomitant treatments).	
Probably	There is evidence to suggest a causal relationship and the influence of other	
	factors is unlikely.	
Almost certainly	There is clear evidence to suggest a causal relationship and other possible	
	contributing factors can be ruled out.	

Events that are assessed as being "possibly", "probably" or "almost certainly" related will be reported as having a reasonable possibility of being related, and events assessed as "unrelated" or "unlikely" will be reported as having no reasonable possibility of being related.

Assessment of causality should be made based on known safety profiles of the product (dornase alfa / hypertonic saline) or SmPC/PIL and known risk profiles of other drugs in the same class. If any doubt about the causality exists, the local investigator should inform the LCTC who will notify the Chief Investigators. In the case of discrepant views on causality between the treating investigator and others, the opinion of the treating investigator will never be downgraded and the MHRA will be informed of both points of view.

11.5 Assessment of "Expectedness"

The Chief Investigators for the CF STORM trial are responsible for determining whether a safety event is expected or unexpected, however a Chief Investigator will not assess their own patients, these patients will be assessed by the other Chief Investigator. There is no requirement for a reporting investigator to assess expectedness.

An event will be considered unexpected if it is not listed within the current and approved RSI for the product at the time of the event's onset. The nature, severity, or frequency of the event should be considered – if this

IRAS ID: 293186 Page **41** of **63**

is not consistent with that described for the type of event in the RSI the event should be assessed as unexpected.

11.5.1 Reference Safety Information (RSI)

Dornase alfa is the CF STORM IMP. The following document will be used as its RSI and used to assess expectedness of SARs:

 Dornase alfa – Summary of Product Characteristics – Pulmozyme 2500 U/ 2.5 ml, nebuliser solution-Section 4.8.

Hypertonic Saline is a CE-marked medical device (not an IMP) being used for its intended purpose in CF STORM. The following document will be used as its RSI and used to assess expectedness of Related SAEs:

• Hypertonic saline – Patient Information Leaflet – PulmoClear Sterile 7% Hypertonic Sodium Chloride Solution, 'Side effects' section.

11.6 Time Period for Active Monitoring of Safety Events

IMPORTANT: Any safety events occurring after the end of the below described "active monitoring" period which meet the definition of serious (see section 11.2) and are recorded for this study must continue to be reported by sites to LCTC in accordance with the timeframes and procedures described in section 12. The same processes established for SARs and Related SAEs within the active monitoring period should be followed for these events.

Active monitoring of safety events experienced by trial participants will be from the period of randomisation until the study completion visit.

Pregnant women will be followed up until the study completion visit with the patient (see Section 11.8 for more information on reporting pregnancy).

11.7 Notes on Safety Event Recording

CF STORM is a low-risk CTIMP trial. Expedited safety reporting will be limited to death and related safety event (SAR for dornase alfa / Related SAE for hypertonic saline) reporting, however adverse event data (complications) will be collected and specifically monitoring by the IDSMC for:

- A pulmonary exacerbation managed with intravenous (IV) antibiotics (in hospital or home)
- An absolute fall in percent predicted forced expiratory volume in one second (ppFEV₁) >10% predicted between consecutive encounters

In the case of pulmonary exacerbation managed with IV antibiotics, or a drop in ppFEV₁ >10%, the encounter will need to be recorded on the UK CF Registry within 4 weeks of the event date (site investigators will be encouraged to enter in a timely manner). Note, pulmonary exacerbation managed with IV antibiotics (in hospital or home) or a drop in ppFEV₁ >10% do not constitute a SAE/R, see Section 11.2 Assessment of Seriousness.

- The following events will not be captured during the study as adverse events Acute courses of oral antibiotics
- An increase in frequency or intensity of a pre-existing episodic event/condition
- A condition (even though it may have been present prior to the start of the trial) detected after randomisation
- Laboratory abnormalities in liver function tests that require clinical intervention or further investigation (unless they are associated with an already reported clinical event).

IRAS ID: 293186 Page **42** of **63**

- · Injury or accidents
- · Pregnancy (See section 11.8 for more details)

Hypertonic saline is categorised as a CE marked medical device and therefore any event which meets the definition of "serious" and is "probably", "possibly" or "almost certainly" related to the hypertonic saline (Related SAE) will be recorded and reported to the LCTC in the same way as a SAR for the purposes of this protocol. If the event is deemed to be related but not expected this will be recorded at LCTC as a Related Unexpected Serious Adverse Event (RUSAE). LCTC will inform the site of any new RUSAEs and the site should report the RUSAE in line with their internal procedures.

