11.1 Terms and Definitions

Adverse Event (AE)

Any untoward medical occurrence in a patient or clinical trial subject administered a medicinal product and which does not necessarily have a causal relationship with this treatment.

An AE can therefore be any unfavourable and unintended sign (including an abnormal laboratory finding, for example), symptom or disease temporally associated with the use of a medicinal product, whether or not considered related to the medicinal product.

Adverse Reaction (AR)

Any untoward and unintended response to an investigational medicinal product related to any dose administered.

An AE which is assessed to be "probably", "possibly" or "almost certainly" related to the trial IMP dornase alfa will be classed as an AR.

Serious Adverse Event (SAE)

Any untoward medical occurrence or effect that at any dose results in death, is life-threatening, requires hospitalisation or prolongation of existing hospitalisation, results in persistent or significant disability or incapacity, or is a congenital anomaly or birth defect.

Serious Adverse Reaction (SAR)

An AR which meets the definition of serious (see Section 11.2) is a Serious Adverse Reaction (SAR). A SAR that has been assessed as "expected" (see Section 11.5 Expectedness) according to the Reference Safety Information (see below) will remain classified as a SAR only, however some SARs that are considered 'unexpected' will be further classified as a Suspected Unexpected Serious Adverse Reaction (SUSAR) (see below).

Suspected Unexpected Serious Adverse Reaction (SUSAR)

An AR that is classed in nature as serious and "unexpected" (i.e. not listed within the Reference Safety Information (RSI) approved for the trial by the MHRA and current at the time of onset of the SUSAR).

Related Adverse Event (Related AE)

An AE which is assessed to be "probably", "possibly" or "almost certainly" related to the hypertonic saline is classed as a Related AE.

N.B. this definition does not include events related to the trial's IMP dornase alfa – such events are classed as ARs (see above).

IRAS ID: 293186 Page **39** of **63**

Related Serious Adverse Event (Related SAE)

An SAE which is assessed to be "probably", "possibly" or "almost certainly" related to the hypertonic saline is classed as a Related SAE.

N.B. this definition does not include events related to the trial's IMP dornase alfa – such events are classed as SARs (see above).

Related Unexpected Serious Adverse Event (RUSAE)

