12.1.1 Flowchart for Site Reporting Requirements of Adverse Events

12.1.2 Reporting Safety Events to the LCTC

All safety events (whether or not assessed as "serious" / "related" / "expected") should be recorded on the UK CF Registry under the "Complications tab". Intravenous antibiotics (dates and duration) and decline >10% in ppFEV $_1$ between consecutive encounters will be recorded on the UK CF Registry within 4 weeks of the event.

Safety events which are assessed as "serious" and "related" must **also** be recorded in more detail on the "SAR form" which can be found within the CF STORM Module; a single form is used for each individual event

IRAS ID: 293186 Page **44** of **63**

(i.e. a single diagnosis), though multiple symptoms can be recorded. *N.B. this includes events assessed as either "related" to the dornase alfa IMP (i.e. SARs) and events assessed as "related" to the hypertonic saline trial procedure (i.e. Related SAE).*

Where additional information is received by site after initial submission to LCTC, this should be updated on the "SAR form" within 5 days. The "SAR form" collects data regarding the nature of event, date of onset, severity, corrective therapies given, outcome and causality; all serious events reported to LCTC will be reviewed by a Co-Chief Investigator and assessed for causality and expectedness.

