12.2 Investigator Reporting Responsibilities

The PI is responsible for ensuring that all safety events requiring recording on this study (see section 12.1) which the local research team becomes aware of are reported to LCTC. It is the responsibility of the PI/Co-I as recorded on the Delegation Log (medically qualified person) to assess the seriousness and causality of events. When documenting any adverse events, the correct medical terminology must be used in accordance with MedDRA.

All safety events must be recorded on the "Complications tab" within seven days of the site team becoming aware of the event.

Safety events which meet the definition of "serious" and "related" must be reported in more detail to the LCTC on the "SAR form" and reported **immediately and in no circumstances later than 24 hours from becoming aware** where they will be appropriately processed.

The "SAR form" should be completed by an appropriately delegated member of the research team; the assessments of seriousness and causality must be performed by an appropriately medically qualified person. Minimum reporting information* must be provided in initial reports for all studies.

The minimum information* required for reporting is as follows:

- Valid EudraCT number
- Sponsor trial number
- One identifiable coded subject
- One identifiable reporter
- One safety event
- One suspect product (including active substance name)
- A causality assessment.

Safety events should also be reported to the site R&D team in accordance with local policy.

REPORTING AN INITIAL OR FOLLOW-UP SAR / Related SAE

The investigator should ensure the actions below are completed for all reportable SARs / Related SAEs:

IRAS ID: 293186 Page **45** of **63**

- 1) The complication (AE) should be marked as 'serious' on the CF STORM Module.
- 2) The LCTC will receive an alert email to alert them that the SAR criteria has been met (only for AEs assessed as "serious" and "related").
- 3) The responsible investigator will then complete the "SAR form" within the CF STORM Module and provide sign off (immediately, within 24 hours).
- 4) The LCTC will receive an alert email to notify them that a "SAR form" has been completed.
- 5) The responsible investigator must notify their R&D department of the event (as per standard local governance procedures).
- 6) The patient must be identified by trial number **only**. The patient's name **should not** be used on any correspondence.

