14.2 Data Collection Methods

The UK CF Registry is the primary data collection instrument for the trial. Data entered routinely in the UK CF Registry will be used alongside CF STORM Module's specific data fields in order to collect the data required. The UK CF Registry is a web-based remote data entry system that captures information for each CF visit (encounter). Data should be entered on an encounter basis, clinics should aim to enter data on the UK CF Registry and manually transfer the data over to the CF STORM Module within three weeks of an encounter and certainly no later than six weeks after the encounter. Where centre staff are aware of a SAR/Related SAE, data should be entered more promptly in line with the SAR reporting timelines specified in section 12.2 of the protocol. Training will be provided to sites for the CF STORM Module prior to any data entry.

14.3 **Monitoring**

Monitoring is conducted to ensure protection of patients participating in the trial and all aspects of the trial (procedures, trial intervention administration and data collection) are of high quality and conducted in accordance with sponsor and regulatory requirements.

A detailed Trial Monitoring Plan will be developed and agreed by the TMG and CI to describe who will conduct the monitoring, at what frequency monitoring will be done, and what level of detail monitoring will be conducted. This will be dependent on the documented risk assessment of the trial which determines the level and type of monitoring required for specific hazards. All processes may be subject to monitoring, e.g. enrolment, consent, adherence to trial interventions, accuracy and timeliness of data collection etc.

Trial Oversight Committees related to the monitoring of the trial are detailed in Roles and Responsibilities see section 4.

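### The ppFEV1 safety count compares consecutive encounters only, so a gradual loss well above 10 points can go uncounted; sections 11.7 and 11.2 also disagree on when an exacerbation is serious

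*Protocol*

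**What the plan says.** Section 11.7 lists two events for specific IDSMC monitoring. One is "A pulmonary exacerbation managed with intravenous (IV) antibiotics (in hospital or home"). The other is an absolute fall in ppFEV1 ">10% predicted between consecutive encounters". Section 12.1.2 keeps the same reference point: IV antibiotic use and such declines "between consecutive encounters will be recorded on the UK CF Registry within 4 weeks of the event".

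Encounter spacing is not fixed; section 10.7 leaves follow-up to routine consultations. Section 13.3 plans no formal interim analysis of primary or secondary outcomes. It lists safety data among what the IDSMC reviews at least annually.

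On seriousness, section 11.7 adds a sentence beginning "Note, pulmonary exacerbation managed with IV antibiotics (in hospital or home) or a drop in" ppFEV1 above 10%. It states that these are not a SAE or SAR and refers the reader to section 11.2. Section 11.2 says that "hospitalisations for pulmonary exacerbations, including prolonged existing hospitalisation for pulmonary exacerbation, do not constitute a SAE", as part of its hospitalisation criterion.

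On timing, section 12.2 requires every safety event to be entered on the Complications tab "within seven days of the site team becoming aware of the event". Sections 11.7 and 12.1.2 allow 4 weeks from the event.

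**The concern.** This is a withdrawal trial, and one objective in section 9.2 is to identify adverse events tied to a large loss of respiratory function. The likely harm from stopping may build up slowly. A rule that resets its reference at every encounter detects sudden falls and is weak against slow ones. A participant could end far more than 10 points below baseline and contribute nothing to the named safety count. Gradual decline would still enter the primary and longitudinal ppFEV1 analyses, but those come at the end of the trial. At stake is whether the IDSMC's by-arm safety data can show such a pattern while it can still act on it.

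The seriousness wording is a separate matter. Section 11.7 relies on section 11.2 but states a broader exclusion, so two sites could classify the same event differently.

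**Working it through.** **The rule by arithmetic.** The protocol gives no detection rate for its trigger, so there is no stated figure to reproduce. A fall of exactly 10 points or less per interval is not counted. The largest uncounted total is 10 × k points over k intervals: 20, 30 or 40 points over 2, 3 or 4 intervals. A loss of 8 + 8 + 8 = 24 points is never counted.

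**Simulation.** From the protocol: the 10-point threshold, the consecutive comparison and 52 weeks of follow-up. Assumed, because the protocol does not give them: baseline plus four equally spaced encounters, a linear loss of L points by week 52, and independent measurement noise with within-person SD s of 2 to 5 points. The model is y(t) = −L·t + e(t), with e(t) ~ N(0, s²), t = 0, ¼, ½, ¾, 1 and 400,000 patients per setting.

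- Consecutive rule: any y(previous) − y(current) > 10.
- Baseline comparison: any y(0) − y(t) > 10.

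| s | L = 12, consecutive | L = 12, from baseline | L = 0, consecutive | L = 0, from baseline |
|---|---|---|---|---|
| 2 | 2.6% | 79.2% | 0.1% | 0.1% |
| 3 | 19.0% | 75.2% | 3.6% | 3.1% |
| 4 | 39.6% | 73.8% | 15.0% | 11.5% |
| 5 | 55.7% | 74.0% | 29.5% | 21.3% |

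For a true 20-point loss, the consecutive rule flags 15%, 43% and 75% at s = 2, 3 and 5. The baseline comparison flags 100%, 99.5% and 96%. With no noise, neither the 12-point nor the 20-point steady loss is ever flagged by the consecutive rule.

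**Hand check at s = 3, L = 12.** Each step has mean fall 12/4 = 3 and SD 3√2 = 4.243. P(step > 10) = 1 − Φ((10 − 3)/4.243) = 1 − Φ(1.65) ≈ 0.0495. Treating the four steps as independent, 1 − (1 − 0.0495)⁴ ≈ 0.184, close to the simulated 0.190. At week 52 alone, the fall from baseline has mean 12 and the same SD. P(> 10) = Φ((12 − 10)/4.243) = Φ(0.471) ≈ 0.68, and the earlier encounters raise this to the simulated 75%.

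**Seriousness, side by side.** Section 11.2 lists death, threat to life, hospitalisation, disability, congenital anomaly and other important medical events. Its waiver for exacerbations sits inside the hospitalisation item only. Section 11.7 excludes IV-treated exacerbations and ppFEV1 drops above 10% with no such limit. A life-threatening or disabling IV-treated exacerbation is thus serious under section 11.2 and not serious under section 11.7.

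**Timing, side by side.** A ppFEV1 fall measured in clinic can be known to the site on the day. Section 12.2 then gives 7 days, and sections 11.7 and 12.1.2 give 28: a difference of 21 days for the same event.

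**The case against.** The strongest reply is that little is lost. Spirometry is recorded at encounters when performed, longitudinal ppFEV1 is a secondary outcome, and clinicians may alter treatment or discontinue the allocation at any stage (sections 8.5 and 10.8.1). The IDSMC sees results by arm, is asked to weigh safety alongside efficacy, and may have further displays set in its charter, which is not at hand. This stands as far as it goes: the gap is a missing aggregate count during the trial, not missing data or unobserved patients. It does not change how the protocol defines the event named for monitoring. The simulation's SDs, visit count and linear decline are also assumptions, so only the direction and rough size of the gap can be relied on.

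A reader might infer more than the protocol supports:

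- *That serious harm from exacerbations is missed.* IV-treated exacerbations are collected and named for IDSMC review, and section 11.9 requires all deaths to be reported. The issue is classification.
- *That more visits always make a decline harder to flag.* From four to six encounters with a 12-point loss, the consecutive rule goes from 19.0% to 16.9% at s = 3, but from 55.7% to 60.9% at s = 5, where noise adds flags.
- *That harm in STOP is hidden because reactions are tied to the products, or that these two events are the IDSMC's main view of it.* An event "related to the trial IMP dornase alfa will be classed as an AR" describes a product reaction and naturally arises in those taking it. Section 12.3.1 separately provides safety events by arm. No extra causality category is needed to make the present point.
- *That three deadlines conflict.* The time in section 14.2, "within three weeks of an encounter and certainly no later than six weeks after the encounter", is the general rule for routine encounter data. The 4-week rule is specific to these two events. Only the 7-day and 4-week times overlap, and even they run on different clocks: awareness and event.

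It can also be said that section 11.7, by citing section 11.2, merely restates the hospitalisation waiver. That may be the intention, but the sentence as written is unconditional.

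**Conclusion.** The point holds in a limited form. The only ppFEV1 safety event is a fall between consecutive encounters, and a gradual loss well above 10 points can go uncounted in the IDSMC's safety data during the trial. That follows from the definition without any assumption. Its size depends on the assumed model: for a steady 12-point loss over four intervals, about 3% to 56% are flagged against 74% to 79% from baseline, across SDs of 2 to 5. The baseline comparison gives no more false flags at any of these SDs. The primary analysis is unaffected. The conflict between sections 11.7 and 11.2 is textual and certain. The overlap between the 7-day and 4-week times is a smaller ambiguity.

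**What to change.** 1. Derive centrally, from ppFEV1 already held on the registry, the number of participants with an absolute fall of more than 10 points from their randomisation baseline at any encounter. Show it to the IDSMC by arm, beside the consecutive-encounter count. This is a monitoring tabulation only and implies no change to patient management.
2. Reconcile the seriousness sentence in section 11.7 with section 11.2, so that the status of a life-threatening or disabling exacerbation is unambiguous. Which classification applies is for the sponsor and the investigators to settle.
3. Reconcile the 7-day time in section 12.2 with the 4-week time in sections 11.7 and 12.1.2 for these two events, stating from what date each clock runs.

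The cost is one derived variable, a slightly longer IDSMC report and a wording amendment. No new assessments are needed.

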12 REPORTING REQUIREMENTS

12.1 Reporting Procedures

All safety events which are recorded for the study should be reported following the procedures detailed below. The occurrence of a safety event may come to the attention of research staff during routine study visits, from the participant's notes, directly from the participant or by other means. Note that reporting procedures vary dependent on the nature of the incident (i.e. "serious" events are to be reported to LCTC in an expedited manner). Any questions concerning adverse event reporting should be directed to the LCTC in the first instance. A flowchart is given below to aid in determining reporting procedures for different types of adverse events.

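### Section 11.7 excludes conditions detected after randomisation from adverse event capture, which contradicts 11.6, 12.1.2 and 12.2

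*Protocol*

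**What the plan says.** Protocol section 11.7 limits expedited reporting to deaths and related serious events. It states that adverse event data (complications) will nevertheless be collected, and names two events for specific IDSMC monitoring. It then introduces a list with the words "The following events will not be captured during the study as adverse events". One bullet in that list is "A condition (even though it may have been present prior to the start of the trial) detected after randomisation". The others are acute oral antibiotic courses, worsening of pre-existing episodic conditions, certain liver-test abnormalities, injuries or accidents, and pregnancy.

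Section 11.6 runs active safety monitoring from randomisation to the study completion visit.

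Section 12.1.2 says: "All safety events (whether or not assessed as 'serious' / 'related' / 'expected') should be recorded on the UK CF Registry", and names the Complications tab as the place. Section 12.2 adds: "All safety events must be recorded on the 'Complications tab' within seven days of the site team becoming aware of the event". Neither sentence mentions the exclusions in 11.7.

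**The concern.** A condition first detected after randomisation is a central part of what adverse event recording in a trial is meant to find. If 11.7 is taken at its word, a site need not record it; if 12.1.2 and 12.2 are taken at their word, the site must record it within seven days. A site cannot comply with both.

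At stake is the completeness of the safety data. Section 12.3.1 plans safety reports by site and arm, and section 13.3 has the IDSMC review safety data at least annually. If sites resolve the conflict differently, those tables will mix sites that record new conditions with sites that do not, and nothing in the data will show which is which. The trial now recruits from age 6, so the same uncertainty applies to children's data.

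**Working it through.** No figure in the protocol bears on this point, so there is nothing to recalculate. The check is a comparison of the sections.

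1. **Is it an exclusion list?** The only header over the bullet is the not-captured sentence. The same list holds oral antibiotic courses, which are collected as a secondary outcome (9.2), and pregnancy, which it sends to 11.8. Those items make sense only as exclusions, so the bullet is an exclusion as written.

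2. **What does the bullet cover?** It has no limit by seriousness, relatedness or date of onset. The parenthesis widens it: conditions already present are included as well as new ones.

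3. **Over what period?** The exclusion starts at randomisation, and so does active monitoring under 11.6. The two periods coincide.

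4. **Does it fall within the adverse event definition?** Section 11.1 covers any untoward medical occurrence, including signs, symptoms, laboratory findings and disease. A newly detected condition is inside that definition. The definition is wider than the bullet, because an isolated symptom or acute reaction is not plainly a detected condition. The bullet therefore removes a large class of events, but not demonstrably all of them.

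5. **Does section 12 limit itself to what 11.7 leaves?** Section 12.1 opens with "All safety events which are recorded for the study should be reported following the procedures detailed below", and 12.2 describes the investigator's duty as covering "all safety events requiring recording on this study (see section 12.1". Both phrases suggest that scope is set elsewhere. But 12.2 points to 12.1 and not to 11.7, and within 12.1 the operative rule (12.1.2) is that all safety events are recorded. The chain of references never reaches the 11.7 list.

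6. **What is recorded regardless of the bullet?**

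| Event | Own rule |
|---|---|
| Deaths | 11.9 |
| Serious events related to dornase alfa or hypertonic saline | 11.7, 12.1.2, 12.2 (SAR form within 24 hours) |
| IV-treated exacerbations; ppFEV1 falls above 10% | 11.7, 12.1.2 (within 4 weeks) |
| Hospital stays | 9.2, 10.7 |
| Pregnancy | 11.8 |

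Hospital stays are collected as numbers of stays and days, so a stay can be counted without its cause being assessed as an adverse event. What remains is non-serious events and non-fatal serious events judged unrelated. Their only general route is the Complications tab.

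7. **Can serious related events be missed?** The duty to report them does not depend on 11.7. The procedure in 12.2, however, begins with marking the complication as serious; the alert to the coordinating centre and the SAR form come after that. A site that never enters the condition as a complication may not reach the first step. This is a possibility, not a certainty.

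8. **What happens to the comparison between arms?** Section 6 stratifies the 1:1 randomisation by site. A site that follows 11.7 literally under-records in both arms, so differences between sites should be roughly balanced. The expected effect is fewer recorded events and weaker ability to see a difference.

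**The case against.** The strongest reply is that 11.7 sets scope and section 12 sets procedure, in a Type A trial of marketed products that deliberately limits safety reporting. On this reading the phrases about events recorded for, or requiring recording on, the study take their meaning from 11.7. The safety objective in 9.2 is confined to large falls in lung function and IV-treated exacerbations, and both are captured explicitly. The flowchart in 12.1.1 might also settle the matter; it could not be read in the text available.

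Part of this stands. The low-risk rationale may well explain leaving out injuries, liver-test abnormalities and worsening episodic conditions, so their presence in the list is not in itself an error. It does not explain the post-randomisation bullet. Section 11.7 applies the low-risk argument to expedited reporting and then says adverse event data will be collected, which is hard to square with excluding newly detected conditions.

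A reader might go further and infer that sites will record almost nothing beyond IV-treated exacerbations, ppFEV1 falls and deaths. The rules listed above show otherwise. A reader might also infer that the comparison between arms will reflect which section each site followed. Stratification by site argues against that. The trial is open label, so discretion left to sites could in principle be used differently by arm, but nothing in the protocol shows that it would be or in which direction.

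**Conclusion.** The contradiction is real and rests on the wording alone. As written, 11.7 excludes conditions detected after randomisation, while 11.6 monitors from randomisation and 12.1.2 and 12.2 require every safety event to be recorded.

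The loss falls mainly on non-serious events and on non-fatal serious events judged unrelated, with some risk that serious related events are missed because their first recording step is never taken. The size cannot be estimated: the protocol gives neither expected adverse event rates nor any indication of how sites read the rule. The expected consequence is incomplete and inconsistent data for the IDSMC, not a directional bias. That conclusion assumes a site applies one reading to both of its arms.

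The likeliest explanation is a drafting slip. The remark that a condition may have been present beforehand makes sense in a rule about what to include, and so does the exception attached to the liver-test item. This is an inference, and the protocol does not support reading the bullet as a deliberate decision to drop new-onset events. The amendment chronology in section 18 names no change to 11.7.

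**What to change.** Remove or reword the post-randomisation bullet in 11.7 so that newly detected conditions are captured, and make 11.7 agree with 11.6, 12.1.2 and 12.2.

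Have the sponsor state whether each of the other exclusions (worsening episodic conditions, liver-test abnormalities, injuries) is intended. Those that are confirmed can stay, but 12.1.2 and 12.2 should then refer to them, because a rule covering all safety events contradicts them too. Check the 12.1.1 flowchart against the result, and send sites a short memo stating which events go on the Complications tab.

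The cost is amendment wording, the memo, and some additional Complications-tab entries.
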